## **9.2. Safety Measurements**

### **9.2.1. Physical Examination,**

Physical examinations are to be performed at each study center visit. Complete physical examinations are to be performed at the time points designated in [Table 1](#). The complete physical examination includes assessment of the following:

- General appearance
- Head, eyes, ears, nose, and throat
- Cardiovascular system
- Respiratory system
- Gastrointestinal system (abdomen)
- Lymphatic system
- Musculoskeletal system
- Skin

- Psychiatric
- Neurological – A complete neurologic examination, including assessment of mental status, memory, cranial nerves, motor function, and reflexes, is to be performed as part of the complete physical examination.

Targeted (i.e., symptom-directed) physical examinations are to be conducted at the time points designated in [Table 1](#).

Abnormal physical examination findings that are considered by the Investigator to be clinically significant are to be reported as an AE, if the finding represents a change from baseline.

#### **9.2.2. Height and Weight**

Height is to be measured for all patients during Screening.

Body weight is to be measured during Screening and at the time points designated in [Table 1](#). The patient's height documented during Screening and weight documented prior to the commencement of tinostamustine on Day -1 are to be used to calculate the tinostamustine dose.

#### **9.2.3. ECOG Performance Status**

ECOG performance status is to be determined at the time points designated in [Table 1](#). The ECOG performance status scale, with corresponding Karnofsky performance status score equivalents, is presented in [Table 4](#).

**Table 4: Eastern Cooperative Oncology Group Performance Status Scale, with Equivalent Karnofsky Performance Status Scores**

ECOG 		Karnofsky 	
Score	Criterion	%	Criterion
0	Normal activity	100	Normal; no complaints; no evidence of disease
		90	Able to carry on normal activity; minor signs or symptoms of disease
1	Symptoms but ambulatory	80	Normal activity with effort; some signs or symptoms of disease
		70	Cares for self; unable to carry on normal activity or do active work
2	In bed <50% of time	60	Requires occasional assistance but is able to care for most of his/her needs
		50	Requires considerable assistance and frequent medical care
3	In bed >50% of time	40	Disabled, requires special care and assistance
		30	Severely disabled; hospitalization is indicated though death is not imminent
4	100% bedridden	20	Very sick; hospitalization is necessary
		10	Moribund; fatal processes progressing rapidly
5	Dead	0	Dead

#### 9.2.4. Vital Signs

Vital signs, including blood pressure, pulse and respiration rates, and body temperature, are to be measured at the time points designated in [Table 1](#). Pulse rate and blood pressure will be measured with the patient in a sitting position after a 5-minute rest.

Vital signs abnormalities that are considered by the Investigator to be clinically significant are to be reported as AEs, if the finding represents a change from baseline.

### **9.2.5. Holter Monitoring**

Continuous Holter monitoring will be performed on Day -1, the day of tinostamustine administration. Holter monitoring will commence 15 minutes prior to the start of the infusion on Day -1 and will continue through 24 hours following the end of infusion.

Patients should be resting comfortably in the supine or semisupine position for 15 minutes prior to each of the following timepoints: 0 [before start of infusion] then after start of the infusion at 15, 30, 45, 60 and 75 minutes and 3, 6, and 24 hours following the start of the infusion.

At time 0 and at all time points after infusion, ECGs readings will be extracted for establishment of baseline and for the purposes of Dose Limiting Toxicities determination and for cardiac safety analyses.

The Holter monitor flashcards will be sent to eResearch Technology, Inc., for processing. The analysis methodology will be described in a separate ECG cardiac safety statistical analysis plan.

Note that because the ECG recordings are stored on flashcards, results will not be available in “real time” at the study center.

The ECGs extracted from the Holter monitoring will be used for the determination of DLTs.

### **9.2.6. 12-Lead Electrocardiogram**

A triplicate ECG will be performed during Screening to determine patient eligibility for the study. Furthermore, on Day -1 (-1 day), a triplicate ECG is to be performed before study drug administration and a single ECGs will be performed at 30 and 60 minutes after the start of study drug administration for assessment by the site. Another single ECG will be performed at visit on D30 ( $\pm$  5 days). ECGs are to be repeated by the Investigator, as clinically indicated.

ECGs (12-lead) are to be performed in after the patient is supine for 5 minutes.

All screening ECGs will be reviewed centrally. Regarding other 12-lead ECGs: the Investigator or the Sponsor may request expedited central review of ECGs, as clinically indicated. ECGs will be reviewed centrally. The Investigator or the Sponsor may request expedited central review of ECGs, as clinically indicated.

The Investigator’s interpretation of ECGs is to be used for patient management during the study; the central reader interpretation of ECGs extracted from Holter monitoring will be used to determine all ECG data for study endpoints including baseline QTcF interval for cardiac safety analyses and DLTs.

## **9.2.7. Safety Laboratory Tests**

### **9.2.7.1. Hematology, Serum Chemistries, and Urinalysis**

Blood samples are to be collected for assessment of hematology, coagulation studies, and clinical chemistry parameters and urine samples for urinalysis, according to the schedule defined in [Table 1](#). Laboratory samples are to be collected after vital signs are measured.

The following safety laboratory parameters will be measured:

#### **Hematology**

- Hematocrit
- Hemoglobin
- Red blood cell count
- White blood cell count
- Platelet count
- Neutrophils
- Lymphocytes
- Monocytes
- Eosinophils
- Basophils

#### **Serum Chemistries**

- ALT
- AST
- Bilirubin (total, direct, and indirect)
- Magnesium
- Glucose
- Phosphate
- Sodium
- Creatinine\*
- Uric acid
- Alkaline phosphatase
- Bicarbonate
- Calcium
- Chloride
- Lactate dehydrogenase
- Potassium
- Total protein
- Blood urea nitrogen

\*To be fractionated if abnormal.

#### **Coagulation Studies**

- Prothrombin time and/or International normalized ratio
- Activated partial thromboplastin time

## Urinalysis

- Color
- Specific gravity
- Glucose
- Blood
- pH
- Protein
- Ketones

Safety laboratory tests may be repeated as necessary during treatment at a schedule determined by the Investigator, based on the patient's clinical status.

Laboratory abnormalities that are considered by the Investigator to be clinically significant are to be reported as AEs, if the finding represents a change from baseline.

## 9.2.8. Adverse Events

### 9.2.8.1. Definitions

#### 9.2.8.1.1. Adverse Event

An AE is defined in the ICH Guideline for GCP as "any untoward medical occurrence in a patient or clinical investigation patient administered a pharmaceutical product and that does not necessarily have a causal relationship with this treatment" (ICH E6:1.2).

Worsening of a pre-existing medical condition, (i.e., diabetes, migraine headaches, gout) should be considered an AE if there is either an increase in severity, frequency, or duration of the condition or an association with significantly worse outcomes.

Interventions for pretreatment conditions (i.e., elective cosmetic surgery) or medical procedures that were planned before study enrollment are not considered AEs.

In the case of death, only record "Fatal" for the event causing death. AEs that are ongoing at the end of the study or time of death are to be noted as "continuing." Classification of AEs is to be done by the Investigator according to the NCI CTCAE, version 4.03.

The Investigator is responsible for reviewing laboratory test results and determining whether an abnormal value in an individual patient represents a significant change from baseline. In general, abnormal laboratory findings without clinical significance (based on the Investigator's judgment) should not be recorded as AEs; however, laboratory value changes requiring therapy are considered AEs.

#### 9.2.8.1.2. Suspected Adverse Reaction

A suspected adverse reaction is any AE for which there is a reasonable possibility that the drug caused the AE. For the purposes of safety reporting, "reasonable possibility" and/or at least possibly related means there is evidence to suggest a causal relationship between the drug and

the AE. A suspected adverse reaction implies a lesser degree of certainty about causality than adverse reaction, which means any AE caused by a drug.

#### *9.2.8.1.3. Serious Adverse Event*

An AE or suspected adverse reaction is considered “serious” if, in the view of either the Investigator or Sponsor, it results in any of the following outcomes:

- is fatal
- is life-threatening (i.e., places the patient at immediate risk of death)
- requires in-patient hospitalization or prolongation of existing hospitalization
- results in persistent or significant disability/incapacity
- is a congenital anomaly/birth defect
- is an important medical event. An important medical event is an event that may not result in death, be life-threatening, or require hospitalization but may be considered an SAE when, based upon appropriate medical judgment, it may jeopardize the patient and may require medical or surgical intervention to prevent one of the outcomes listed in the definitions for SAEs. Examples of such medical events include allergic bronchospasm requiring intensive treatment in an emergency room or at home, blood dyscrasias or convulsions that do not result in inpatient hospitalization, or the development of drug dependency or drug abuse.

A hospitalization meeting the regulatory definition for “serious” is any inpatient hospital admission that includes a minimum of an overnight stay in a health care facility. Any AE that does not meet one of the definitions of serious (i.e., emergency room visit, outpatient surgery, or requires urgent investigation) may be considered by the Investigator to meet the “important medical event” criterion for classification as an SAE.

#### *9.2.8.1.4. Unexpected Adverse Event*

An AE or suspected adverse reaction is considered “unexpected” if it is not listed in the Investigator’s Brochure or is not listed at the specificity or severity that has been observed; or, if an Investigator’s Brochure is not required or available, is not consistent with the risk information described in the General Investigational Plan or elsewhere in the current application, as amended.

#### **9.2.8.1.5. Serious and Unexpected Suspected Adverse Reaction**

A serious and unexpected suspected adverse reaction (SUSAR) is any event that meets all 3 of the following definitions:

- 1) suspected adverse reaction ([Section 9.2.8.1.2](#));
- 2) serious ([Section 9.2.8.1.3](#)); and
- 3) unexpected ([Section 9.2.8.1.4](#)).

#### **9.2.8.2. Adverse Event Assessment**

All AEs will be collected and recorded from the time written informed consent is obtained through Day 100 ( $\pm 7$  days), or after the end of the study, if thought to be related to study drug. This includes AEs the patient reports spontaneously, those observed by the Investigator, and those elicited by the Investigator in response to open-ended questions during scheduled study visits.

Each AE is to be assessed by the Investigator with regard to the following categories.

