### **6.6. Study Completion**

A patient is considered to have completed the study if they complete the Day 100 ( $\pm 7$  days) visit and a confirmatory response assessment between D107 visit and D130 visit, the latest.

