### 9.2.8.4. Reporting Serious Adverse Events

SAEs will be collected and recorded throughout the study period, beginning with the signing of the informed consent form (ICF) through the Day 100 ( $\pm 7$  days) visit, or after the end of the study if thought to be related to study drug.

The Investigator must report all SAEs to the Sponsor within 24 hours of discovery.

A completed SAE report is to be sent to the Medical Monitor's attention within 24 hours of discovering the event. The initial report should include at least the following information:

- Patient's ID number;
- Description and date of the event;
- Criterion for serious; and

- Preliminary assignment of causality to study drug.

The Medical Monitor will contact the Investigator via telephone for follow-up information regarding the SAE, as appropriate.

The Investigator, or designated party, should notify the appropriate IRB/EC of SAEs occurring at the study center and other AE reports received from the Sponsor, in accordance with local procedures and statutes.

SAEs that are considered as possible or probably related to the investigational product, and as unexpected (i.e., SUSARs), will be reported to the concerned Competent Authorities (CAs) and IRBs/ECs by the Sponsor or Sponsor's designee as required by applicable local regulations. Per regulation, any fatal or life-threatening SUSAR will be reported to the CAs/IRBs/ECs within 7 calendar days, and additional information within an additional 8 calendar days. The Sponsor or Sponsor's designee is required to submit any other SUSAR to the CAs/IRBs/ECs within 15 calendar days of notification. The Sponsor or its designee is also responsible for notifying the investigational sites of all expedited SAEs. The Investigator must keep copies of all expedited SAE information including correspondence with the Sponsor on file.

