*9. Women who are pregnant or breastfeeding, or plan to become pregnant or breastfeed, are not eligible for study participation.*

**Item 9:** End of trial definition, Synopsis Pg.12

Currently, Protocol Version 2.0 18 June 2018 does not contain a clear and unambiguous definition of end of trial. In the protocol synopsis (Pg. 12) under “Duration of Treatment and Study Duration” the following text will be added: *The end of trial will be the last patient last visit (LPLV).*

**Item: 10:** Summary of known and potential risks and benefits to human subjects

Currently, Protocol Version 2.0 18 June 2018 does not include a summary of known and potential risks and benefits to human subjects. The following text will be added in a protocol amendment as new section 4.3 “Risks and Benefits” in the protocol:

*This study is investigating the use of Tinostamustine*

*On the sister study, Tinostamustine is being tested the first in human study in patients with relapsed or refractory haematological malignancies for which there are no available approved therapies. Preliminary signals show that the treatment with tinostamustine may offer benefit by overcoming tumor resistance and trigger response. As a result, this therapy may slow down or stop disease progression. Out of 37 patients evaluable for efficacy during the dose-escalation part of the study, approximately half have benefited from treatment.*

*The risks associated with the treatment with tinostamustine are expected to be similar to other alkylators, like bendamustine. The peripheral cell compartments show a differential sensitivity to tinostamustine, with lymphocytes being most sensitive and platelets most robust, but showing the most rapid decline at higher doses. Due to myelosuppression, patients may be more susceptible to infections. The analysis of the chemistry data showed no other meaningful or serious organ toxicity. ECGs during and after infusion showed small prolongations of the QTc interval during and post infusion. Mean change from baseline were up to 24 ms and were clinically not significant. Blood pressure and heart frequency showed no notable changes in any subjects at any dose levels. Patients may experience various types of gastrointestinal toxicity such as nausea, vomiting or diarrhea. At the studied doses these events were non-severe. Mundipharma-EDO considers the benefit and risk balance to be in favour of further development of this molecule in humans.*

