**Possible Risks Include:**

- Myelosuppression (thrombocytopenia, leukopenia, and neutropenia)
- Anemia

- *Gastrointestinal symptoms (nausea, vomiting, diarrhea, constipation)*
- *Cough*
- *Peripheral edema*
- *Pyrexia*
- *Decreased appetite*
- *Dyspnea*
- *Headache*
- *Asthenias*
- *Allergic reaction*
- *Infection*
- *QTc Prolongation*

*As noted above, the risks associated with the treatment with Tinostamustine are expected to be similar to other alkylators, like bendamustine. Additionally, patients undergoing any high-dose conditioning for transplant, will experience myelosuppression, which puts the patients at a higher risk for infection. Thus, the protocol was designed around current standard practices for monitoring the toxicity and safety of patients in this treatment setting. Patients are evaluated daily for hematologic parameters, signs of infection, and any other adverse reactions until engraftment is reached. After engraftment the patients are monitored monthly through 130 days but may be seen in between these timepoints if clinically indicated. Cardiac safety is monitored pre-infusion through 24 hours post infusion with a continuous holter monitor, in addition to ECGs being performed and read by the qualified site personnel before, during, and after the infusion. Other adverse reactions will be continuously monitored and treated as appropriate according to the protocol and local standard of care.*

*Since the purpose of this study is to evaluate the safety and preliminary efficacy of this regimen, it is unknown if this treatment will benefit individual patients directly. While the study may or may not improve the disease of the patients, they could benefit in the following ways:*

- *Helping others by contributing to medical research*
- *Monitoring of their condition while on the study with additional study services and evaluations.*

*While this investigational agent and regimen are being studied, the ongoing sister studies have shown some early promising results. Preliminary data shows that treatment with this agent may offer benefit by overcoming tumor resistance and trigger response. As a result, this therapy may slow down or stop disease progression. Therefore, Mundipharma-EDO considers the benefit and risk balance to be in favour of further development of this molecule in humans.*

**Item 11:** Very good partial response (VGPR), Synopsis Pg.4; Pg. 34 Section 3.2.1.1

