#### A. Adverse Events

Per the protocol, Adverse Events will be collected from the time written informed consent is obtained through Day 100 ( $\pm 7$  days), or after the end of the study, if thought to be related to study drug, and will be defined as Treatment-Emergent Adverse Events (TEAE). Any events occurring prior to the tinostamustine dose are part of the subject's baseline status and will be recorded on the Medical History form.

If the start date of an adverse event is missing, the site will be queried to obtain the missing date. If that attempt is unsuccessful, the following rules will be applied to impute the start date of an adverse event:

- If the day (or the day and the month) are missing, but all other date components match with the first dose date of study drug, use the first dose date of study drug.
- If the day (or the day and the month) are missing, but some of the other date components do not match with the first dose date of study drug, use the earliest possible date. For example, use Jan 1 if the day and the month are missing; use the first day of the actual month if only the day is missing.
- If the day, month, and year are missing, use the first dose date of study drug, as long as the adverse event end date is not prior to the first dose date of study drug. Otherwise, do not impute.

AEs will be coded using MedDRA, associating lower-level terms with preferred terms and system organ classes by the primary hierarchy. The tables will display counts and percentages of patients who reported at least one AE in each system organ class represented in the AE data. Within each system organ class, the tables will display the counts and percentages of patients reporting at least one AE, as designated by the preferred terms. AE summaries will include treatment-emergent AEs (TEAEs).

Summary tables of TEAEs by default MedDRA System Organ Class (SOC) and Preferred Term (PT) will be sorted by decreasing order of frequency of SOC, and then, within that, by decreasing order of frequency of PT in the All Subjects group.

The following AE summary tables displaying counts and percentages of patients with adverse events will be produced:

- All TEAEs by Preferred Term.

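### A new drug-related adverse event between the Day 100 visit and the patient's completion of the study falls in neither collection window, and outside the SAP's definition of a treatment-emergent event

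*Protocol*

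**What the plan says.** **Collection.** Protocol 9.2.8.2 states: "All AEs will be collected and recorded from the time written informed consent is obtained through Day 100" (±7 days), and then adds "or after the end of the study, if thought to be related to study drug". Section 9.2.8.4 sets the same two periods for serious events, from signature of the consent form through the Day 100 visit, "or after the end of the study if thought to be related to study drug".

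**Recording.** Section 9.2.8.3 has events entered in the source documents and eCRF up to the Day 100 visit. The adverse event row of Table 1 also stops at Day 100. Neither extends to later related events. The D130 column of Table 1 holds only M-protein, immunoglobulin and free light chain tests.

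**End of participation.** Under section 6.6 a patient completes the study with the Day 100 visit and "a confirmatory response assessment between D107 visit and D130 visit, the latest". Item 5 of the 21 September 2018 memo confirms D107 to D130. The version 2.0 synopsis gives a maximum follow-up of 130 ±7 days after transplant. Item 10 of the 14 December 2018 memo says, as part of the risk description: "After engraftment the patients are monitored monthly through 130 days".

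**Analysis.** SAP VIII.A repeats the two periods, "or after the end of the study, if thought to be related to study drug, and will be defined as Treatment-Emergent Adverse Events".

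**The concern.** The two periods join only if the study ends at the Day 100 visit, and the protocol places the end later. A related event that starts after the patient has left the study is to be collected. The same event at, say, Day 115, in a patient still due for the confirmatory assessment, is not. That is unlikely to have been intended.

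Two things are at stake. First, sites that apply the wording literally would not enter a late related event, while sites that apply the likely intent would, so capture could differ across the up to 18 planned centers. Second, the SAP inherits the gap, because the TEAE tables are defined by the same periods. SAP I.C drops several of the protocol's other safety analyses, including dose-limiting toxicities, engraftment failure and treatment-related mortality. The adverse event tables are therefore among the main safety summaries that remain.

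**Working it through.** No sample size, power or error rate is involved, and the plan gives no figure of its own to reproduce. The check sets the passages side by side and then does date arithmetic.

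**Which text covers a new related event with onset at Day 115, before the confirmatory assessment?**

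| Provision | Covers it? | Reason |
|---|---|---|
| 9.2.8.2 and 9.2.8.4, first period | No | Closes at the Day 100 visit (Day 93 to 107) |
| 9.2.8.2 and 9.2.8.4, second period | No | Opens only once the study has ended |
| 9.2.8.3, eCRF recording | No | Stops at the Day 100 visit |
| Table 1, adverse event row | No | Stops at Day 100 |
| 9.2.8.5, follow-up of events | No | Sets how long events are followed; gives no collection window for new onsets |
| SAP VIII.A, TEAE definition | No | Uses the same two periods |
| 9.2.8.4, reporting within 24 hours | If serious | No Day 100 limit stated |
| 9.2.8.6, IRB/EC reporting | If fatal, or serious and possibly related | No Day 100 limit stated |
| 7.5.1, Safety Committee review of continuing patients | In general terms | Says safety data are collected, without stating what is recorded or when |

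**Length of the gap**, taking the end of the study as the patient's own completion:

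gap = day of completion − day of the Day 100 visit

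Inputs: the Day 100 visit falls on 100 ± 7, so Day 93 to Day 107. Completion falls on D107 to D130 (section 6.6; September 2018 memo, Item 5). Under the synopsis wording of 130 ± 7, the latest day is 130 + 7 = 137.

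- Shortest: 107 − 107 = 0 days (late Day 100 visit, confirmation at the first permitted day).
- Nominal: 130 − 100 = 30 days.
- Longest under D107 to D130: 130 − 93 = 37 days.
- Longest under 130 ± 7: 137 − 93 = 44 days.

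If the second period instead opened at the Day 100 visit for related events, the uncovered interval would be 0 days in every case.

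**The case against.** **The intent is plain.** The authors probably meant through Day 100, or later if related. Section 9.2.8.4 opens with "SAEs will be collected and recorded throughout the study period", which supports a wider reading. This is fair as a guess at intent. But the same sentence then closes that period at the Day 100 visit, and reading the end of the study as Day 100 contradicts section 6.6, the September memo and the synopsis. The text should say what was meant.

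**Serious events are caught elsewhere.** This largely stands. The 24-hour duty in 9.2.8.4, the IRB/EC duty in 9.2.8.6 and the Safety Committee review in 7.5.1 carry no Day 100 limit. It would be wrong to say that late deaths or serious related events escape reporting. What remains is new non-serious related events, and whether related serious events reach the eCRF and the TEAE tables.

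**The SAP would list the event anyway.** This stands in part. SAP V.K lists all recorded data, VIII.A includes a listing of all adverse events, and V.B applies no analysis windows. A recorded event would therefore be listed. It would still fall outside the TEAE definition, and the recording rule does not call for it to be entered.

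**Stronger readings that a reader might infer, and that the documents do not support:**

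- *A gap of years for early patients.* Item 9 of the December 2018 memo defines the end of the trial as last patient last visit (LPLV). If the adverse event sections meant that, the gap for the first patients would run through most of the planned 2.5 to 3.5 years. But section 6.6 defines completion patient by patient, nothing equates the two terms, and nearly all of that time would fall after the patient had left the study.
- *A gap of at least 23 days.* The figure 130 − 107 = 23 assumes confirmation at D130. Confirmation is allowed from D107, so the minimum is 0.
- *A link to the safety halt.* SAP I.C says that the study was stopped on safety signals, but gives no timing and does not connect them to events after Day 100.

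**Conclusion.** The gap is real on the wording and small in extent. A new related event between the Day 100 visit and the patient's completion lies outside both collection periods, outside the eCRF recording rule and Table 1, and outside the TEAE definition. The exposure is 0 to 37 days per patient (nominally 30, and up to 44 under 130 ±7 days).

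The conclusion rests on two assumptions: that the end of the study means the patient's own completion under section 6.6, and that sites apply the sentence as written. The gap would be longer only if LPLV were meant, and would vanish only if the Day 100 visit were meant, which conflicts with section 6.6. How many events are affected cannot be estimated, because the documents give no rate of new related events after Day 100. This is a drafting fault worth correcting; it does not show that serious late toxicity went unreported.

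**What to change.** 1. In 9.2.8.2 and 9.2.8.4, replace the second period with wording that collects events at any time after the Day 100 visit when they are considered drug-related.
2. Bring 9.2.8.3 and the adverse event row of Table 1 into line, so that such events are recorded in the eCRF.
3. Change the sentence in SAP VIII.A to match, so that related events after Day 100 enter the TEAE tables.

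The cost is a phrase in two protocol sections, matching edits in one more section and one table row, and one SAP sentence. No extra visit is needed, and no sample size or power figure moves. Extending any-cause collection of serious events and deaths to D130 is not needed to close this gap. A contact at D130 itself is also not guaranteed, since confirmation may take place from D107.

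SAP I.B allows changes until database lock, but a SAP change alone can bring in only events that sites recorded. If the protocol wording was in force throughout, the study report should say that entry of related events after Day 100 was not clearly required.
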